1.1. Synopsis

Protocol Title: A Randomized, Placebo-Controlled, Participant- and Investigator-Blind, Phase 1 Study to Evaluate the Pharmacokinetics, Safety, and Tolerability of LY3832479 Administered Subcutaneously to Healthy Participants

Short Title: A Randomized, Placebo-Controlled, Phase 1 Study to Evaluate the Pharmacokinetics, Safety, and Tolerability of LY3832479 Administered Subcutaneously to Healthy Participants

Rationale: The clinical program for LY3832479 so far has involved IV dosing of LY3832479.

Study PGAB will investigate SC dosing of LY3832479. Single SC doses of LY3832479, 350 mg and 1000 mg, will be administered to establish the PK, safety, and tolerability profiles in healthy participants.

Objectives and Endpoints

Objectives	Endpoints
Primary	
To determine the PK of single SC doses of LY3832479 in healthy participants	AUC(0-∞) and C _{max}
Secondary	
To describe safety and tolerability following single SC doses of LY3832479 in healthy participants	Incidence of spontaneously reported AEs, TEAEs, and SAEs; vital signs; clinical laboratory results

Abbreviations: AE = adverse event; AUC(0-∞) = area under the concentration versus time curve from time 0 to infinity; C_{max} = maximum observed drug concentration; ISR = injection site reaction; PK = pharmacokinetics; SAE = serious adverse event; SC = subcutaneous; TEAE = treatment-emergent adverse event.

Overall Design

This is a single-site study in healthy participants who will receive a single SC dose of LY3832479. The study will be participant- and investigator-blinded, randomized, and placebo controlled.

Disclosure Statement: This is a PK and safety study to test LY3832479 and placebo in up to 2 dose cohorts.

[figure not shown]
Number of Participants:

A maximum of 22 participants, in 2 cohorts of at least 9 participants, will be enrolled to study intervention with the intention that at least 6 participants randomized to LY3832479 have sufficient evaluable data in each cohort.

Intervention Groups and Duration:

This is a single-dose study with an estimated duration for each participant of up to 16 weeks from screening through follow-up. Participants will be screened within 14 days prior to Day 1 of dosing for each cohort, with an allowable window of up to 28 days.

Data Monitoring Committee: No

1.2. Schema

Abbreviations: LY = LY3832479; PBO = placebo; SC = subcutaneous.

1.3. Schedule of Activities (SoA)

Procedure / Assessments	Screening	Treatment Period							Follow-up Visits				Comment	
Visit Number	V1	V2							V3	V4	V5	V6/ ED		
Week(s)		0							2	4	8	12		
Study Day	-14 to -1	-1	1	2	3	4	5	6	7	15 ±2d	29 ±3d	60 ±3d	85 ±3d	
Informed consent (written)	X													
Review/confirm I/E criteria	X	X												After screening, ensure participants continue to meet I/E criteria.
Medical history including pre-existing conditions	X													
Weight/height	X											X		Height at screening only.
Urinalysis	X							X						
COVID-19 clinical screening	X	X							X	X	X	X		Symptoms and recent contact (see Section 5.2 for a description of symptoms and close contact). At designated timepoints and as needed during the study.
SARS-CoV-2 serology		X							X	X	X	X		Serology results are not needed before dosing.

Procedure / Assessments	Screening	Treatment Period							Follow-up Visits				Comment	
		V1	V2							V3	V4	V5	V6/ED	
Visit Number	Week(s)	0							2	4	8	12		
Study Day	-14 to -1	-1	1	2	3	4	5	6	7	15 ±2d	29 ±3d	60 ±3d	85 ±3d	
SARS-CoV-2 point-of-care test	X	X									Additional point-of-care tests may be conducted at the investigator's discretion. See Section 8.3.7.			
Naso-pharyngeal swab			X								Can be before or after LY3832479 administration. For research purposes. See Section 8.3.7.			
Nasal swab				X							For research purposes. This swab may be taken if a point-of-care test is done during the study, as described in Section 8.3.7.			
Admission to study site		X												
Discharge from study site								X						
Physical examination Medical assessment	X	X	Predose		X			X	As needed			X	Full PE/MA at screening and Visit 6/ED. Symptom-directed PE/MA at all other indicated time points and as deemed necessary by the investigator or designee.	

Procedure / Assessments	Screening	Treatment Period									Follow-up Visits				Comment
		V1	V2							V3	V4	V5	V6/ED		
Visit Number		0							2	4	8	12			
Week(s)									2	4	8	12			
Study Day	-14 to -1	-1	1	2	3	4	5	6	7	15 ±2d	29 ±3d	60 ±3d	85 ±3d		
Vital signs: blood pressure, body temperature, pulse rate ^a	X	X	Predose	24 h (±2 h)		X			X	X	X	X	X		Vital signs should be taken following at least 5-min rest in a supine position. Vital signs may be taken any time prior to dosing. If screening takes place on Day -1, there is no need to take vital signs twice on Day -1.
Single 12-lead ECG	X												X		ECG should be taken following at least 5-min rest in a supine position.
Concomitant medications review	X	X								X	X	X	X		
AE review	X	X	Predose	X	X	X	X	X	X	X	X	X	X		AEs to be reviewed only after participant has signed the study ICF.
HIV, hepatitis B/C serology	X														

Procedure / Assessments	Screening	Treatment Period							Follow-up Visits				Comment	
		V1	V2							V3	V4	V5	V6/ED	
Visit Number	Week(s)	0							2	4	8	12		
Study Day	-14 to -1	-1	1	2	3	4	5	6	7	15 ±2d	29 ±3d	60 ±3d	85 ±3d	
Pregnancy test (women only) ^b		X	X										X	Serum pregnancy test at screening, urine test at other timepoints. Day -1 urine test refers to test at admission; this is not needed if admissions is on the same day as screening. Postdose urine test(s) can be performed at the judgment of the investigator, if pregnancy is suspected.
Clinical laboratory tests ^a		X	X						X	X	X	X	X	Fasting is not required for these tests. If screening takes place on Day -1, there is no need to conduct these tests twice on Day -1.
Breath or urine ethanol screen			X											Ethanol screen may be repeated at other time points at the discretion of the investigator.
Urine drug screen		X	X											Day -1 urine test refers to test at admission; this is not needed if admission occurs on the same day as screening. Drug screen may be repeated at other time points at the discretion of the investigator.

Procedure / Assessments	Screening	Treatment Period							Follow-up Visits				Comment	
Visit Number	V1	V2							V3	V4	V5	V6/ ED		
Week(s)		0							2	4	8	12		
Study Day	-14 to -1	-1	1	2	3	4	5	6	7	15 ±2d	29 ±3d	60 ±3d	85 ±3d	
SC LY3832479 or placebo dosing			X											
LY3832479 PK sampling ^a			X	X	X	X	X	X	X	X	X	X	X	Day 1 collection should be 4-8h postdose. The exact time of draw must be recorded. For Day 2 onwards, PK samples may be taken at any time after vital signs.
Injection site assessments ^c			Predose; 1min ±1min, 10min ±2min, 30min ±5min, 240min ± 10min	24h ±4h	X	X	X	X	X					Timepoints include ISR assessment, VAS, if pain is reported, and the exploratory Scarletred tool. Scarletred timing is flexible and not confined to the windows shown, except for predose. See Section 8.2.6 for detail.
Immunogenicity			Predose							X	X	X	X	
Serum sample for exploratory biomarkers ^a			Predose		X					X	X	X	X	
Pharmacogenetics sample ^a			Predose											For storage only.

Abbreviations: AE = adverse event; COVID-19 = Coronavirus disease-2019; ECG = electrocardiogram; ED = early discontinuation; h = hours; HIV = human immunodeficiency viruses; I/E = inclusion/exclusion; ICF = informed consent form; MA = medical assessment; ISR = injection site reaction; min = minutes; PE = physical examination; PK = pharmacokinetics; SARS-CoV-2 = severe acute respiratory syndrome coronavirus 2; SC = subcutaneous; V = visit; VAS = visual analog scale.

- a When conducted on the same day, the order of procedures should be vital signs, ECG, and then blood sampling.
- b For women who are considered to be postmenopausal, follicle-stimulating hormone should be drawn to confirm postmenopausal status if necessary, according to Appendix 4 (Section 10.4).
- c In case an ISR is still present on Day 29, additional ISR assessments will be performed at subsequent visits. In case an ISR is present on an early discontinuation visit, an ISR assessment should be performed at this visit.

2. Introduction

2.1. Study Rationale

The clinical program for LY3832479 so far has involved IV dosing of LY3832479 to healthy participants.

Study PGAB, will investigate SC dosing of LY3832479. Single SC doses of LY3832479, 350 mg and 1000 mg, will be administered to establish the PK, safety, and tolerability profiles in healthy participants.

2.2. Background

The viral pathogen causing the COVID-19 pandemic is the SARS-CoV-2. Viral entry into host cells involves its structural Spike glycoprotein. The Spike glycoprotein attaches itself via its RBD to the human ACE2, enabling sufficient proximity for the virus to fuse with the target cell membrane. Angiotensin-converting enzyme 2 is expressed in the membrane of various cell types in a variety of tissues, primarily in the lung, small intestine, kidney, and vascular endothelium (Hamming et al. 2004; Human Protein Atlas Project [WWW]). There are no approved therapies to date for the treatment of COVID-19; Remdesivir and convalescent plasma are available under an emergency use authorization in the United States (FDA 2020 [WWW]; Gilead Sciences 2020).

LY3832479 is a neutralizing IgG-1 mAb that specifically binds the Spike glycoprotein RBD with high affinity, preventing its interaction with the ACE2 human receptor. This in turn blocks viral cell fusion, preventing SARS-CoV-2 invasion of human cells, inhibiting viral replication. As the binding epitope of LY3832479 to RBD covers the most conserved RBD/ACE2 interaction site based on an analysis of the LY3832479-RBD complex x-ray structure, LY3832479 is expected to neutralize all currently described viral strains.

The amino acid sequence of recombinant antibody LY3832479 was derived from human memory B cells of a convalescent patient with COVID-19. Point mutations (L234A, L235A; LALA mutation) were introduced into the Fc domain of the native human IgG1 antibody to eliminate Fc effector function, to reduce the risk of ADE.

Preclinical experience with LY3832479

Serum drug concentrations have been obtained up to study Day 57 in Study PGAA. Based on these preliminary data, the observed PK is consistent with previous model predictions (based on allometric scaling from monkey PK); and the mean half-life is expected to be in the range of 22 to 25 days. The current data also indicate the PK to be dose-proportional. Preliminary PK data from Study JS016-001-I also appeared to be similar to that of Study PGAA.

Additional information can be found in the IB.

2.3. Benefit/Risk Assessment

There is no anticipated therapeutic benefit for the participants.

The maximum planned dose of LY3832479 in this study is 1000 mg SC. This is lower than the maximum dose delivered IV in previous studies.

Potential risks related to SC injections of LY3832479 are as follows:

- Hypersensitivity reactions and ISRs: Study participants will be in-house for the first 7 days after dosing, which will enable close monitoring for hypersensitivity reactions and ISRs post-injection.
- Antibody-dependent enhancement of viral replication in case any of these healthy volunteers contract a SARS-CoV-2 infection while they still have significant LY3832479 exposure after dosing: This phenomenon has been observed with some other viruses including the dengue virus, but is only a theoretical risk without clinical evidence in the case of respiratory coronaviruses (Graham 2020). In addition, LY3832479 was specifically engineered to avoid this risk as explained in Section 2.2.

- Unknown risks related to on-target and off-target toxicity. These risks are low due to the
 - fact that LY3832479 targets a foreign protein
 - human origin of LY3832479 (the LALA mutations do not involve the RBD of LY3832479), and
 - absence of binding in the TCR studies performed in humans and monkeys.

Given the totality of data on LY3832479, the overall benefit/risk assessment of this study is considered favorable.

More detailed information about the known and expected benefits and risks and reasonably expected AEs of LY3832479 may be found in the IB.

3. Objectives and Endpoints

Objectives	Endpoints
Primary	
To determine the PK of single SC doses of LY3832479 in healthy participants	AUC(0-∞) and C _{max}
Secondary	
To describe safety and tolerability following single SC doses of LY3832479 in healthy participants	Incidence of spontaneously reported AEs, TEAEs, and SAEs; vital signs; clinical laboratory results
Exploratory	
To assess ISRs following single SC doses of LY3832479 in healthy participants	Characterization and measurement of incidence and severity of ISRs (including injection site pain) using data collected from the ISR assessment, as well as the exploratory tool (Scarletred)
To determine the immunogenicity of LY3832479 following single SC doses in healthy participants	Incidence of TEADA

Abbreviations: AE = adverse event; AUC(0-∞) = area under the concentration versus time curve from time 0 to infinity; ISR = injection site reaction; PK = pharmacokinetics; SAE = serious adverse event; SC = subcutaneous; TEADA = treatment-emergent antidrug antibodies; TEAE = treatment-emergent adverse event.

4. Study Design

4.1. Overall Design

This is a single-site study in healthy participants who will receive a single SC dose of LY3832479. The study will be participant- and investigator-blinded, randomized, and placebo controlled.

4.1.1. Screening and Enrollment

Up to 2 cohorts may be enrolled with at least 9 participants per cohort (7 LY3832479:2 placebo), with the intention that at least 6 participants randomized to LY3832479 have sufficient evaluable data in each cohort.

Participants will be screened within 14 days prior to Day 1 of dosing for each cohort, with an allowable window of up to 28 days (see Section 5.4). Participants will be admitted to the CRU as part of an inpatient visit on Day -1 and will be sequentially enrolled and then randomized to treatment.

4.1.2. Inpatient Stay

Participants will be admitted to the study site on Day -1. They will remain inpatient until discharge on Day 7 after study procedures are complete.

Dosing

Dosing will occur on Day 1. Intended doses of LY3832479 are as follows:

- Cohort 1: 350 mg
- Cohort 2: 1000 mg

See Section 6.1 for detail of injection volumes.

Participants will undergo PK sampling and safety assessment after dosing.

For Cohort 1, a safety review will be conducted to determine whether it is appropriate to proceed with dosing of the next cohort. This safety review will be conducted based on data from at least 5 participants assigned to LY3832479, after at least 4 days after dosing.

Postdose sampling

On Days 1 through 7, participants will undergo PK sampling and safety assessment as shown in the SoA (Section 1.3).

4.1.3. Outpatient Follow-Up

Follow-up visits will be conducted through Day 85, as shown in the SoA (Section 1.3).

In the event a participant has suspected or confirmed SARS-CoV-2 infection, follow-up visits may be conducted at the participant's home.

4.2. Scientific Rationale for Study Design

This is the first study to evaluate a new formulation of LY3832479 (125 mg/mL in 20 mM L-histidine pH 6.0, 8.04% sucrose, 0.05% polysorbate 80, and water for injection) in humans via SC administration. This study will be conducted with healthy participants, rather than patients with COVID-19, because the important biopharmaceutic questions related to the new SC route of administration, such as PK and tolerability, will be more efficiently investigated in the healthy human population.

The 4-day safety review together with inpatient status after dosing is sufficient to detect an acute adverse systemic response that would preclude dose escalation.

Placebo will be used as a comparator to allow interpretation of safety and tolerability data following administration of LY3832479.

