6.6.1. Dose-Escalation Criteria

Data will be evaluated on an ongoing basis.

After at least 5 participants assigned to LY3832479 have completed Day 4 in a given cohort, all safety data available up to this cutoff date (AEs and vital signs) will be reviewed to determine whether the next cohort can be randomized after agreement between Lilly's medical monitor and the investigator. Safety and tolerability data will be the primary criteria guiding dose escalation.

The investigator and the Lilly sponsor team are responsible for determining any dose decisions. The investigator(s) will remain blinded and the Lilly sponsor team will be unblinded during these reviews. All available data from Cohort 1 will be reviewed. Depending on the results of the safety evaluation, the dose of Cohort 2 may potentially be decreased, but not increased beyond the planned maximum dose of 1000 mg.

If temporary stopping criteria are met (Section 6.6.3), dosing will be temporarily halted and no further participants will be dosed until a full safety review of the study has taken place.

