8.2.2. Vital Signs

For each participant, vital sign measurements should be conducted according to the SoA (Section 1.3). Additional vital signs may be measured during each study period at the investigator's judgment. Blood pressure and pulse rate should be measured after at least 5 minutes supine.

Orthostatic vital signs should be assessed, if possible, during any AE of dizziness or posture-induced symptoms. If orthostatic measurements are required, participants should be supine for at least 5 minutes and stand for at least 3 minutes. If the participant feels unable to stand, supine vital signs only will be recorded.

Additional vital signs may be measured during each study period, if warranted.

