8.3.1. Time Period and Frequency for Collecting AE and SAE Information

All AEs and SAEs will be collected from the time of signing of the ICF until participation in the study has ended.

Adverse events that begin before the start of study intervention, but after signing of the ICF will be recorded on the AE CRF.

Although all AEs after signing the ICF are recorded by the site in the CRF/electronic data entry, SAE reporting to sponsor begins after the participant has signed the ICF and has received study intervention. However, if an SAE occurs after signing the ICF, but prior to receiving study intervention, it needs to be reported within the SAE reporting time frame if it is considered reasonably possibly related to study procedures.

All SAEs will be recorded and reported to the sponsor or designee immediately and under no circumstance should this exceed 24 hours, as indicated in Section [10.3](#), Appendix 3. The investigator will submit any updated SAE data to the sponsor within 24 hours of it being available.

Investigators are not obligated to actively seek AEs or SAEs after conclusion of the study participation (Day 85). However, if the investigator learns of any SAE, including a death, at any time after a participant has been discharged from the study, and he/she considers the event to be reasonably related to the study intervention or study participation, the investigator must promptly notify the sponsor.

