8.3.6. Hypersensitivity Reactions

Many drugs, but particularly biologic agents, carry the risk of systemic hypersensitivity reactions. If such a reaction occurs, additional details describing each symptom should be provided to the sponsor in the Hypersensitivity/Anaphylactic/Infusion-Related Reaction CRF.

Sites should have appropriately trained medical personnel and appropriate medical equipment available when study participants are receiving intervention. It is recommended that participants who experience a systemic hypersensitivity reaction be treated per national and international guidance (Lieberman et al. 2015; Simons et al. 2015).

In the case of generalized urticaria or anaphylaxis, additional blood and urine samples should be collected as described in Section 10.7, Appendix 7, “Recommended Laboratory Testing for Hypersensitivity Events”. Laboratory results are provided to the sponsor via the central laboratory.

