#### **9.4.4 Vital signs**

Vital signs data will be summarized by treatment together with changes from baseline, where baseline is defined as the Day 1 predose assessment. Figures of mean vital signs and mean changes from baseline profiles will be presented by treatment.

Values for individual participants will be listed.

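### No vital signs, AE query or examination is scheduled between the Day 1 dose and Day 2, so the vital-sign endpoint has no planned acute reading on drug or placebo

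*Protocol*

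**What the plan says.** Protocol Section 4.2 rests the case for escalating to Cohort 2 on a short safety review plus the inpatient stay: "The 4-day safety review together with inpatient status after dosing is sufficient to detect an acute adverse systemic response that would preclude dose escalation". Section 6.6.1 describes what that review uses once at least 5 participants on LY3832479 have completed Day 4: "all safety data available up to this cutoff date (AEs and vital signs) will be reviewed". The same section adds that everything available from Cohort 1 will be looked at.

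The SoA (Section 1.3) sets the timing. The vital-signs row shows a predose entry on Day 1, then 24 h with a 2 h window either side, then Days 4, 7, 15, 29, 60 and 85. The AE row begins "AE review X X Predose X", so the Day 1 query is predose and the next is on Day 2. The Day 1 examination is also predose. After dosing, the scheduled Day 1 safety contacts are injection-site assessments at "1min ±1min, 10min ±2min, 30min ±5min, 240min ± 10min". There is also a PK draw at 4 to 8 h.

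Other provisions cover unscheduled events:
- Section 8.2.2: "Additional vital signs may be measured during each study period", at the investigator's discretion.
- Section 8.3.1: "All AEs and SAEs will be collected from the time of signing of the ICF until participation in the study has ended".
- Section 8.3.6: for a systemic hypersensitivity reaction, "additional details describing each symptom should be provided to the sponsor" on a dedicated form.

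On analysis, SAP 9.4.4 takes the Day 1 predose value as baseline and says: "Figures of mean vital signs and mean changes from baseline profiles will be presented by treatment".

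**The concern.** Section 4.2 speaks of acute systemic responses, but the schedule contains no systemic measurement in the acute period. Whatever is learned about blood pressure, pulse or temperature in roughly the first 22 hours depends on someone choosing to take a reading. Such readings tend to follow symptoms and fall at different times in different participants. They therefore give no common time point at which drug and placebo can be set side by side, which is the purpose Section 4.2 gives for including placebo.

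Two uses of the data are affected. Vital signs are a secondary endpoint, and they are one of the two data types that Section 6.6.1 names for the decision to dose Cohort 2. The mean profiles in SAP 9.4.4 will run from predose straight to 24 h. A reader could take a flat line as evidence of no acute change when none was scheduled to be measured. This is the first SC use of LY3832479 and a new formulation (Section 4.2), so the early hours are of some interest even though earlier IV doses were well tolerated.

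**Working it through.** The plan makes no calculation on this point. The check is a reading and count of SoA cells.

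**Step 1: scheduled safety procedures between dosing and Day 2.**

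| Procedure | Day 1 entry | Next scheduled |
|---|---|---|
| Vital signs | predose | 24 h ± 2 h |
| AE review | predose | Day 2 |
| Examination | predose | no Day 2 mark; next mark reads as Day 3 (table layout may be broken) |
| Injection-site assessment | predose, then 1, 10, 30, 240 min | 24 h ± 4 h |

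Systemic measurements scheduled in the interval: 0. Local assessments: 4, in both arms.

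**Step 2: time to the first post-dose vital signs.** 24 − 2 = 22 h and 24 + 2 = 26 h.

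**Step 3: vital-sign sets per participant.** Post-dose entries are Days 2, 4, 7, 15, 29, 60 and 85, which makes 7. Of these, 0 fall before 22 h. By the Day 4 cut-off the scheduled minimum is 2 (24 h and Day 4); unscheduled readings may add to it.

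**Step 4: what could still go unseen.** Under Section 10.3.1 an abnormal vital sign is an AE when the investigator judges it clinically significant. A transient, symptom-free change that nobody measures therefore reaches neither the AE data nor the vital-sign data. A change with symptoms has several routes in: continuous AE collection, the Day 2 query, discretionary vital signs and the hypersensitivity form.

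**Step 5: with readings added at 30 and 240 min.**
- Post-dose sets: 7 + 2 = 9, of which 2 fall before 22 h.
- Sets by Day 4: 2 + 2 = 4.
- Extra sets: 2 × 9 = 18 in a 9-person cohort; 2 × 18 = 36 if both cohorts enrol 9; 2 × 22 = 44 at the cap.

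**Step 6: fit with the PK draw.** The 240 min contact has a window of 230 to 250 min, and the draw opens at 4 h = 240 min. The two can coincide between 240 and 250 min. SoA footnote a already puts vital signs before blood sampling on the same day.

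**The case against.** The strongest reply is that nothing relevant to escalation is shown to be missed. Section 4.2 claims sufficiency only for a response that would preclude escalation. The nearest written thresholds, the halting rules in Section 6.6.3, need either a related AE that is serious or severe, or three or more participants with related, clinically significant AEs of at least moderate grade that do not respond to supportive care. A mild, symptom-free reading meets neither. Staff see each participant four times in the first 4 hours and again for the PK draw. IV doses up to 7000 mg were reported as well tolerated. With a half-life of about 22 to 25 days (Section 2.2), an effect driven by exposure should still be visible at 24 h and Day 4.

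Most of this stands. A reader might infer that the escalation review has no systematic acute data at all, or that the Section 4.2 sentence is wrong. The documents support neither reading. Injection-site assessments are systematic in both arms, AEs are collected throughout, and Section 6.6.1 opens all available Cohort 1 data to the review.

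The reply does not remove the narrower gap. The injection-site data are local, and under Section 8.2.6 solicited reactions become AEs only if serious. Discretionary readings are not a substitute for a common time point.

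It is also fair to say that 2 placebo participants per cohort cannot separate a small vital-sign change from ordinary variation, and that no inferential safety analysis is planned (SAP 9.4.12). A plot with labelled time points also makes the misreading of a flat profile less likely.

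**Conclusion.** The point holds as a gap in scheduled measurement. Between the Day 1 dose and Day 2 the plan schedules no vital signs, AE query or examination, and 0 of 7 scheduled post-dose vital-sign sets fall in the first 22 hours. The vital-sign endpoint and the vital-sign input to the escalation review therefore have no planned acute reading in either arm.

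The consequence is limited. Symptomatic or severe reactions would very likely be captured, no stopping rule is shown to fail, and no endpoint becomes invalid. What would be gained is descriptive safety information at common times, not a precise comparison of drug with placebo.

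This rests on reading the Day 1 entries as predose only, which is clear for vital signs, AE review and examination. The day of the next examination mark is less certain and does not affect the conclusion. It also assumes that no other study document, such as a site manual, requires early vital signs; neither the protocol nor the SAP mentions one. The change is a cheap improvement worth making, not a correction on which the trial depends.

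**What to change.** In the SoA Day 1 cells, add one set of vital signs and one open-ended AE query at the existing 30 min and 240 min injection-site contacts. Time them once per participant from the last injection, because a dose is 2 or 4 injections given over up to 10 minutes. Where the 240 min contact coincides with the PK draw, take vital signs first. In SAP 9.4.4, name 30 min and 240 min among the time points for the summaries, the change-from-baseline tables and the figures. SAP 9.4.4 lists no times at present, so this is a short addition.

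The cost is an SoA edit in an amendment, a line or two in the SAP, and the 2 extra sets per participant counted above. Each set needs the 5-minute supine rest that the SoA already specifies, so a few minutes at a contact that already takes place. No new visit, staff or blood draw is needed, and the sample size is unaffected.
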